#### 5.0 Stratification Factors: None

#### 6.0 Registration Procedures

- 6.1 Patients will be registered to the study when they have consented, met eligibility criteria, and have been logged into the Research Participant Tracking (Ptrax) system.
- 6.2 Treatment on this protocol must commence at Mayo Clinic Arizona or Mayo Clinic Rochester under the supervision of a radiation oncologist.
- 6.3 Radiation oncologist has seen the patient and confirms the patient is a suitable candidate for this study.
- 6.4 Patient questionnaires are available on site.

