12.9 Use of alternating electric therapy: yes vs. no

## 13.0 Follow-up Decision at Evaluation of Patient

13.1 A patient is deemed *ineligible* if after registration, it is determined that at the time of registration, the patient did not satisfy each and every eligibility criteria for study entry. The patient will go off study.

- If the patient received MR and F-DOPA-PET for radiotherapy planning, all data up until the point of confirmation of ineligibility must be submitted.
- If the patient never received pre-RT F-DOPA-PET, on-study material must be submitted.

13.2 Those patients who will *not* receive any radiation treatment *or* who will receive radiation treatment elsewhere will move to Event Monitoring phase and be monitored for survival until 5 years after registration.

13.3 Patients who are CR, PR, REGR, or SD will continue to obtain clinically indicated MRI scans for up to 5 years from registration.

13.4 Patients remain on study until all of the following are confirmed / complete (up to 2 years or patient refusal):

- Radiological progression by central review per RANO criteria
- Clinical progression identified by the treating oncologist
- It is more than 3 months since radiation treatments have been completed, to ensure the radiological evidence is tumor progression versus treatment response
- All follow-up study imaging during the patient visit at the time the above three conditions are met is complete

13.5 Patients who develop PD will go to the event-monitoring phase.

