#### 16.2.2 Sample Size

The one-stage design to be utilized is fully described in Section 16.22. A minimum of 39 evaluable patients will be accrued to this phase-II study unless undue toxicity is encountered. We anticipate accruing an additional 4 patients to account for ineligibility, cancellation, major treatment violation, or other reasons. Maximum projected accrual is therefore 43 patients.

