### 16.5.2 Adverse Event Stopping Rules:

As no reactions to F-DOPA have been reported within Mayo Clinic Rochester, toxicity testing reported in the literature revealed no deleterious effects (section 15.0), no reactions are anticipated. As such, at any point in the enrollment process after 10 or more patients have been enrolled, if more than 10% of these patients enrolled are unable to complete PET scanning due to allergic reactions to the tracer, enrollment will be suspended so that details of each episode can be examined and a trial recommendation will be formulated and presented to the MCCC DSMB. There have been no reports in the literature of the occurrence of NSF in patients with normal renal function. Additionally, we will use the contrast agent gadobenate dimeglumine, which has been shown to have a high safety profile (lower incidence of NSF in patients with renal failure/insufficiency) compared with many other available Gd-based contrast agents. Therefore no reactions are anticipated. As such, if at any time a patient develops NSF enrollment will be suspended so that details of the episode can be examined and a trial recommendation will be formulated and presented to the MCCC DSMB.

Using the hypofractionation approach described in Section 7, previous studies have successfully used hypofractionation without significant increases in acute or late adverse effects. However, some studies with more aggressive, higher daily doses of hypofractionation have reported increased toxicity. Nonetheless, both acute (available at <http://ctep.cancer.gov>) and late toxicity will be monitored continuously as each patient is accrued and follow-up data are accumulated. As such, at any point in the enrollment process after 10 or more patients have been enrolled, if more than 10% of these patients enrolled experience any of the following adverse events *considered to be at least possibly related to treatment*, enrollment will be suspended so the details of each episode can be examined and a trial recommendation will be formulated and presented to the DSMB

- Grade 3 or 4 irreversible CNS toxicity
- Grade 4 non-hematologic, non-CNS toxicity
- Any Grade 5 toxicity

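### The toxicity suspension rule in 16.5.2 counts treatment-related events but divides by everyone enrolled, including patients who have not begun, or never begin, protocol radiotherapy

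*Combined protocol and SAP*

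**What the plan says.** The second part of 16.5.2 covers toxicity of the hypofractionated treatment. It states that "toxicity will be monitored continuously as each patient is accrued and follow-up data are accumulated". The rule applies "at any point in the enrollment process after 10 or more patients have been enrolled", and enrolment is suspended "if more than 10% of these patients enrolled experience any of the following adverse events". The list opens with "Grade 3 or 4 irreversible CNS toxicity" and adds Grade 4 non-hematologic, non-CNS toxicity and any Grade 5 toxicity. Each event must be at least possibly related to treatment. Suspension leads to case review and a recommendation to the DSMB. It does not close the trial.

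The following sections determine who is in that denominator:

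- Section 6.1: "Patients will be registered to the study when they have consented, met eligibility criteria" and they have been logged. No treatment is needed.
- Section 13.2: registered patients who get no radiotherapy, or "who will receive radiation treatment elsewhere will move to Event Monitoring phase and be monitored for survival until 5 years after registration".
- Section 16.2.2: "We anticipate accruing an additional 4 patients to account for ineligibility, cancellation, major treatment violation, or other reasons". This gives 39 evaluable and at most 43 enrolled.
- Sections 16.1.1 and 16.3.1.1: for the primary endpoint, by contrast, a patient must have begun treatment to be counted.

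**The concern.** The numerator and the denominator describe different groups. Only a treated patient can have a radiotherapy-related event, yet the count below the line includes patients waiting for PET and radiotherapy and patients who will never have it on protocol. Every such patient lowers the observed proportion, so the bias runs only towards continued enrolment.

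The rule matters because CNS injury is the harm the protocol itself highlights. Section 1.1 cites hypofractionated series with 50% symptomatic necrosis and with necrosis in 20 of 46 patients, and section 10.4.2 exempts CNS necrosis up to Grade 3 from expedited reporting. The plan already restricts its efficacy denominator to treated patients, but not its safety denominator.

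**Working it through.** The plan gives no target rate or trigger probability for this rule, so there is no stated figure to reproduce.

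**1. Events needed as written.** The smallest whole number above 0.10 × n is 2 at 10–19 enrolled, 3 at 20–29, 4 at 30–39 and 5 at 40–43.

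**2. Effect of untreated patients.** Suppose all 4 spare places go to patients who never begin radiotherapy, leaving 43 − 4 = 39 treated.

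- Four events: 4/43 = 9.3%, no suspension; 4/39 = 10.3%, suspension.
- Five events, needed as written at 43: 5/39 = 12.8% of those treated.
- Ignoring rounding to whole events, 10% of enrolled equals 0.10 × 43/39 = 11.0% of treated.

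**3. Effect of patients still waiting.** Assume 1 month from registration to the end of radiotherapy (not in the documents) and even accrual at the planned 15–20 per year (16.2.3). Then 18 of 20 and 28 of 30 enrolled patients have completed radiotherapy. Two events at 20 enrolled are 2/20 = 10.0% (no suspension) but 2/18 = 11.1%. Three at 30 are 3/30 = 10.0% (no suspension) but 3/28 = 10.7%.

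**4. Chance of suspension before the 43rd enrolment.** Simulated with continuous checking, each patient untreated with probability 4/43, onset assumed uniform 3–12 months after radiotherapy, no deaths, and 1,000 runs per setting:

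| True rate | Accrual per year | Enrolled denominator | Begun-RT denominator | Difference (points) |
|---|---|---|---|---|
| 5% | 15 | 0.075 | 0.128 | 5.3 |
| 5% | 20 | 0.061 | 0.100 | 3.9 |
| 15% | 15 | 0.637 | 0.723 | 8.6 |
| 15% | 20 | 0.525 | 0.637 | 11.2 |
| 20% | 15 | 0.857 | 0.910 | 5.3 |
| 20% | 20 | 0.736 | 0.828 | 9.2 |

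With onset fixed at values from 0.5 to 9 months instead, the gain is about 4–13 points at a true 15% and about 3–5 points at a true 5%. A repeat run put the upper end at 5% nearer 6. If every enrolled patient is eventually treated, so that only waiting dilutes, the gain at 15% shrinks to 0.756 − 0.718 = 3.8 points (15 per year) and 0.662 − 0.616 = 4.6 points (20 per year).

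**5. Short follow-up, for scale only.** At 30 enrolled, 23–25 patients are at least 3 months past radiotherapy and 18–21 are at least 6 months past. The 4 events needed are then 16–17% or 19–22% of those patients. Which figure applies, if either, depends on when these events occur, and the documents do not say.

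**6. A matured denominator as a trigger.** Consider dividing by patients who have had the event or reached 6 months after radiotherapy. Section 16.2 assumes a median survival of 7.5 months. If survival is exponential, 0.5^(6/7.5) = 0.574 live 6 months. Events enter at once, but event-free patients who die earlier never enter. With early events and a true 10% rate, the ratio tends to 0.10 / (0.10 + 0.90 × 0.574) = 0.10 / 0.617 = 16%. In simulation with these deaths, suspension at a true 5% rate rises from about 17–20% as written to about 46–48%.

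**The case against.** The rule is not the only safeguard. Toxicity is monitored continuously, the study chairs with the statistician and the DSMB each review at least twice a year (16.5.1), and adverse events can inform termination (16.2.5). Untreated patients are a modest source of dilution: the allowance of 4 also covers ineligibility and major treatment violations, some of which may occur in treated patients, so 39 treated of 43 is the far end of what was budgeted. The 4-event example also depends on timing. Because checking is continuous, a fourth event at 39 or fewer enrolled would already have suspended enrolment (4/39), so the example needs that event to arrive once 40 are enrolled.

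All of this stands and limits the size of the point. None of it justifies the denominator, because no other safeguard changes it.

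A reader might go further and infer that the rule is blind to late CNS injury, and that it should divide by patients with mature follow-up at the same 10% threshold. The documents do not support that. They give no onset time, and two of the three listed event types are not specifically late. At a true 30% rate, with 4 of 43 untreated, the rule as written still suspends in 94–99% of simulated trials. The matured ratio also over-reads when many patients die early (step 6).

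**Conclusion.** The denominator is wrong for a rule about treatment-related events, and the direction of the error is certain: it under-reads. The size is moderate. With 4 of 43 untreated, a nominal 10% trigger is about 11% of treated patients before rounding. The begun-radiotherapy denominator adds about 4–13 points to the chance of suspension at a true 15% rate. Those points rest on assumed onset times (0.5–9 months), a 1-month lag to radiotherapy, 15–20 enrolments per year and no deaths. The 4/43 against 4/39 comparison needs only the plan's own numbers and the assumption that all 4 spare patients are untreated.

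Dilution of late CNS events by short follow-up is also real, but its amount cannot be fixed from the documents. It warrants better reporting, not a second 10% trigger.

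**What to change.** In the toxicity paragraph of 16.5.2, replace patients enrolled with patients who have begun protocol proton radiotherapy, in both the 10-patient start and the 10% threshold. Leave the PET-allergy rule as it is: section 8.0 takes a patient with a tracer reaction off study before imaging, so a radiotherapy-based count would drop the very patients that rule is about.

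In the monitoring report, add irreversible CNS events against time since radiotherapy, by a method that accounts for early deaths, such as cumulative incidence with death as a competing event. Label it as information for the DSMB. Do not use the ratio of patients with the event or 6 months of follow-up as a trigger.

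The cost is a wording change and one added display. There would be about 3–5 points more suspensions for review when the true rate is 5%. The rule would also open slightly later, once 10 patients have begun radiotherapy. Until then, the continuous monitoring and DSMB review already in the plan apply, as they now do before the tenth enrolment.

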## 16.6 Results Reporting on ClinicalTrials.gov

16.6.1 Initial estimated Primary Completion Date: At study activation, this study will have been registered within the www.ClinicTrials.gov (CT.gov) website. The Primary and Secondary endpoints along with other required information for this study will be reported on CT.gov. For purposes of timing of the CT.gov results reporting, the initial estimated completion date of the primary endpoint of this study is 36 months after the study opens to accrual.

16.6.2 Definition of Primary-Endpoint Completion Date (PCD): The PCD is the date at which the last patient has been followed for 12 months.

### 16.7 Inclusion of Women and Minorities

This study will be available to all eligible patients regardless of race, gender, or ethnic group. There is no information currently available regarding differential effects of this regimen in subsets defined by gender, race or ethnicity, and there is no reason to expect such differences to exist. Therefore, although the planned analyses will, as always, look for differences based on gender and racial groupings, the sample size is not increased in order to provide additional power for such subset analyses. Based on prior studies involving similar disease, we expect about 7% of patients will be classified as minorities by race and about 40% of patients to be women. Expected sizes of racial and gender subsets are shown in the following table:

Accrual Targets			
Ethnic Category	Sex/Gender		
	Females	Males	Total
Hispanic or Latino	1	2	3
Not Hispanic or Latino	16	24	40
Ethnic Category: Total of all subjects	17	26	43
Racial Category			
American Indian or Alaskan Native	1	0	1
Asian	0	1	1
Black or African American	1	2	3
Native Hawaiian or other Pacific Islander	0	0	0
White	15	23	38
Racial Category: Total of all subjects	17	26	43

**Ethnic Categories:** **Hispanic or Latino** – a person of Cuban, Mexican, Puerto Rican, South or Central American, or other Spanish culture or origin, regardless of race. The term “Spanish origin” can also be used in addition to “Hispanic or Latino.”

#### Not Hispanic or Latino

**Racial Categories:** **American Indian or Alaskan Native** – a person having origins in any of the original peoples of North, Central, or South America, and who maintains tribal affiliations or community attachment.

**Asian** – a person having origins in any of the original peoples of the Far East, Southeast Asia, or the Indian subcontinent including, for example, Cambodia, China, India, Japan, Korea, Malaysia, Pakistan, the Philippine Islands, Thailand, and Vietnam. (Note: Individuals from the Philippine Islands have been recorded as Pacific Islanders in previous data collection strategies.)

**Black or African American** – a person having origins in any of the black racial groups of Africa. Terms such as “Haitian” or “Negro” can be used in addition to “Black or African American.”

**Native Hawaiian or other Pacific Islander** – a person having origins in any of the original peoples of Hawaii, Guam, Samoa, or other Pacific Islands.

**White** – a person having origins in any of the original peoples of Europe, the Middle East, or North Africa.

**17.0 Pathology Considerations/Tissue Biospecimens**

N/A

**18.0 Records and Data Collection Procedures****18.1 Submission Timetables****Initial Material(s)**

CRF	Pre-Treatment (Compliance with Test Schedule Section 4.0)
Patient Eligibility	
Demographics	
On-Study	
Adverse Events: Baseline	
Patient Status: Baseline	
Patient Assessments	
MMSE Form	
Patient Questionnaire Booklet	
Concurrent Steroid and Anticonvulsant Treatment Form	
Off Treatment	Submit $\leq$ 2 weeks after registration if withdrawal/refusal occurs prior to beginning protocol therapy

**Test Schedule Material(s)**

CRF	Treatment Phase and Active Monitoring (Compliance with Test Schedule Section 4.0)			Event Monitoring  / Follow-up (Compliance with Test Schedule Section 4.0)
	$\leq$ 4 weeks after each evaluation during RT	$\leq$ 1 week after  F- DOPA- PET scan	End of Treatment	
Radiation Therapy	X		X	
Adverse Event Form (Post Injection of  F- DOPA)		X 		
Radiation Therapy Adverse Event Form (Toxicity)			X 	X 
Off Treatment 	X		X	X
Patient Status Form	X		X	X
Consent Withdrawal 	X	X	X	X

CRF	Treatment Phase and Active Monitoring (Compliance with Test Schedule Section 4.0)			Event Monitoring  / Follow-up (Compliance with Test Schedule Section 4.0)
	$\leq$ 4 weeks after each evaluation during RT	$\leq$ 1 week after $^{18}\text{F}$ - DOPA- PET scan	End of Treatment	
Lost to Follow-up 	X		X	X
Patient Questionnaire Booklet 			X 	X 
Concurrent Steroid and Anticonvulsant Treatment Form			X	X
MMSE			X 	X 
Imaging Form 		X		X

1. Acute toxicity will be assessed during standard of care monitoring by the radiotherapy team during the course of treatment.
2. When applicable.
3. Survey will need to be entered manually if it is not completed electronically
4. Done approximately 15-20 minutes post injection of  $^{18}\text{F}$ -DOPA after scan is completed and if AE observed a second AE assessment is required  $\leq$ 24 hours post injection.
5. Late toxicity will be assessed during standard of care appointments. To be submitted  $\leq$ 2 weeks after each clinically indicated MR scan.
6. Patient will complete a maximum of 6 post-RT QOL evaluations
7. Follow-up is until death or a maximum of 5 years from the time of registration.
8. See Appendix VI.

## 18.2 Data Handling and Record Keeping

### 18.2.1 Confidentiality

Information about study subjects will be kept confidential and managed according to the requirements of the Health Insurance Portability and Accountability Act of 1996 (HIPAA). Those regulations require a signed subject authorization informing the subject of the following:

- What protected health information (PHI) will be collected from subjects in this study
- Who will have access to that information and why
- Who will use or disclose that information
- The rights of a research subject to revoke their authorization for use of their PHI.

(This information is contained within the Mayo IRB Informed Consent Template Section 14)

In the event that a subject revokes authorization to collect or use PHI, the investigator, by regulation, retains the ability to use all information collected prior to the revocation of subject authorization. For subjects that have revoked authorization to collect or use PHI, attempts should be made to obtain permission to collect at least vital status (long term survival status that the subject is alive) at the end of their scheduled study period.

### 18.2.2 Source Documents

Source data is all information, original records of clinical findings, observations, or other activities in a clinical trial necessary for the reconstruction and evaluation of the trial. Source data are contained in source documents. Examples of these original documents, and data records include: hospital records, clinical and office charts, laboratory notes, memoranda, subjects' diaries or evaluation checklists, pharmacy dispensing records, recorded data from automated instruments, copies or transcriptions certified after verification as being accurate and complete, microfiches, photographic negatives, microfilm or magnetic media, x-rays, subject files, and records kept at the pharmacy, at the laboratories, and at medico-technical departments involved in the clinical trial. Source documents are kept in a secure location that is locked and requires approved access.

#### 18.2.3 Case Report Forms

The study case report form (CRF) is the primary data collection instrument for the study. All data requested on the CRF must be recorded. All missing data must be explained. If a space on the CRF is left blank because the procedure was not done or the question was not asked, write "N/D". If the item is not applicable to the individual case, write "N/A". All entries should be printed legibly in black ink. If any entry error has been made, to correct such an error, draw a single straight line through the incorrect entry and enter the correct data above it. All such changes must be initialed and dated. Do not erase or use "white-out" for errors. For clarification of illegible or uncertain entries, print the clarification above the item, then initial and date it. If the reason for the correction is not clear or needs additional explanation, neatly include the details to justify the correction.

#### 18.2.4 Records Retention

The investigator will maintain records and essential documents related to the conduct of the study. These will include subject case histories and regulatory documents.

The investigator will retain the specified records and reports for;

1. As outlined in the Mayo Clinic Research Policy Manual –"Retention of and Access to Research Data Policy" [REDACTED]  
[REDACTED]

### 19.0 Study Finances

**19.1 Costs charged to patient:** Routine clinical care

**19.2 Tests to be research funded:** F-DOPA-PET scan and costs incurred for providing copies of imaging from local MD.

**19.3 Other budget concerns:** None.

**Appendix I****ECOG Performance Status**

ECOG PERFORMANCE STATUS*	
Grade	ECOG
0	Fully active, able to carry on all pre-disease performance without restriction
1	Restricted in physically strenuous activity but ambulatory and able to carry out work of a light or sedentary nature, e.g., light house work, office work
2	Ambulatory and capable of all selfcare but unable to carry out any work activities. Up and about more than 50% of waking hours
3	Capable of only limited selfcare, confined to bed or chair more than 50% of waking hours.
4	Completely disabled. Cannot carry on any selfcare. Totally confined to bed or chair.
5	Dead

\*As published in Am. J. Clin. Oncol.:

The ECOG Performance Status is in the public domain therefore available for public use. To duplicate the scale, please cite the reference above and credit the Eastern Cooperative Oncology Group, Robert Comis M.D., Group Chair.

From [http://www.ecog.org/general/perf\\_stat.html](http://www.ecog.org/general/perf_stat.html)

**Appendix II**  
**The European Organization for Research and Treatment of Cancer quality of life questionnaire**  
**(EORTC QLQ-C30)**

**EORTC QLQ-C30 (version 3)**

We are interested in some things about you and your health. Please answer all of the questions yourself by circling the number that best applies to you. There are no "right" or "wrong" answers. The information that you provide will remain strictly confidential.

Please fill in your initials:

**bbbb**

Your birthdate (Day, Month, Year):

